2. LIST OF ABBREVIATIONS

Abbreviation	Definition
aCSR	abbreviated Clinical Study Report
ADAS	anti-drug antibodies
ADCC	antibody-dependent cell mediated cytotoxicity
AE	adverse event
BMI	body mass index
BOR	best overall response
С	cycle
CBR	clinical benefit rate
CDC	complement dependent cytotoxicity
CI	Confidence interval
CR	complete response
CT	computed tomography
D	day
DLT	dose-limiting toxicity
DOR	duration of response
ECG	electrocardiogram
ECOG	Eastern Cooperative Oncology Group
eCRF	Electronic Case Report Form
EOS	End of Study
ET	Early Termination
FFPE	formalin fixed paraffin embedded
HLA	human leukocyte antigen
IHC	immunohistochemistry
IV	intravenous(ly)
KIR	killer cell immunoglobulin-like receptor
mAb	monoclonal antibody
MedDRA	Medical Dictionary for Regulatory Activities
MRI	magnetic resonance imaging
MTD	maximum tolerated dose
NE	non-evaluable
NCI CTCAE	National Cancer Institute Common Terminology Criteria for Adverse
	Events
NK	natural killer
ORR	objective response rate
PD	pharmacodynamics
PD-L1	programmed death – ligand 1
PFS	progression-free survival
PK	pharmacokinetics
PR	partial response
PT	Preferred term

Response Evaluation Criteria in Solid Tumors

Statistical Analysis Plan: OBI-888-001 Review Status: Final

Version: 2.0 Version Date: 02JUN2022

RP2D recommended phase II dose

SAE serious adverse event SAP Statistical Analysis Plan

SD Stable disease SOC System organ class

SRC Safety review committee

TEAE treatment-emergent adverse event tumor infiltrating lymphocytes

Review Status: Final Version: 2.0 Version Date: 02JUN2022

3. INTRODUCTION

This Statistical Analysis Plan (SAP) covers the statistical analysis and reporting for the protocol OBI-888-001 final version 5.0 (dated 08 May 2020), and electronic case report form (eCRF) production version 5.4 dated 17 Nov 2020.

The Sponsor elected to generate an abbreviated Clinical Study Report (aCSR) focusing on safety and exposure.

4. STUDY OBJECTIVES

4.1 PRIMARY OBJECTIVES

The primary objectives are:

- To evaluate the safety and tolerability of OBI-888 when administered intravenously (IV) to patients with locally advanced or metastatic solid tumors.
- To determine the maximum tolerated dose (MTD) and recommended phase II dose (RP2D) of OBI-888 as monotherapy.

4.2 SECONDARY OBJECTIVES

The secondary objectives are:

- To evaluate the preliminary clinical activity profile (objective response rate [ORR], clinical benefit rate [CBR], duration of response [DOR], and progression-free survival [PFS]) of OBI-888.
- To evaluate the immunogenicity of OBI-888 (anti-drug antibodies [ADAs]).
- To determine the serum pharmacokinetics (PK) and pharmacodynamics (PD) of OBI-888.

4.3 EXPLORATORY OBJECTIVES

Exploratory objectives are:

- To assess antibody-dependent cell mediated cytotoxicity (ADCC) and complement dependent cytotoxicity (CDC).
- To identify potential predictive biomarkers.
- To assess the expression of immune markers including immune checkpoints, in the tumor tissue samples.
- To assess the expression of Globo H and related tumor-associated glycans in the tumor tissue.
- To perform glycan analysis of OBI-888.

5. STUDY DESCRIPTION

5.1 STUDY DESIGN

This is a Phase I/II, open-label, dose escalation and cohort expansion study of OBI-888, a humanized monoclonal antibody (mAb) targeting Globo H, in patients with locally advanced or metastatic solid tumors.

This is a 2-part study. Part A (Dose Escalation) is designed to establish the MTD and RP2D of OBI-888. Part B (Cohort Expansion) is intended to further characterize the safety and clinical activity profile of the RP2D dose of OBI-888 administered as monotherapy in patients with locally advanced or metastatic solid tumors.

5.1.1 PART A-DOSE ESCALATION

The dose escalation part of the study included 3 cohorts of escalating dose levels of 5, 10, and 20 mg/kg, using 3+3 design to identify MTD and RP2D.

Three patients were enrolled at the lowest dose level. If none of the 3 patients experienced a dose-limiting toxicity (DLT), the next cohort of 3 patients were to be enrolled at the next higher dose level. If 1 of 3 patients in the initial dose cohort experienced a DLT, that cohort was expanded to 6 patients. If only 1 of these 6 patients had a DLT, then the next cohort of 3 patients were enrolled at the next higher dose level. If 2 or more patients of the 3-6 patients in a cohort experienced a DLT, dose escalation ceased and that dose level was above the MTD (the highest dose where no more than 1 of 6 patients had experienced at DLT). New patients were enrolled at the previous lower (tolerated) dose level until that cohort had 6 patients. This lower dose level was to be considered the MTD if ≤ 1 in 6 patients had a DLT.

Patients should receive all four planned doses with OBI-888 administered during Cycle 1 to be eligible for DLT evaluation, unless they experienced a DLT with any dose. A patient who withdrew from the study within the DLT evaluation period for reasons other than drug-related adverse event (AE) was not included for DLT evaluation and was to be replaced; but could continue to receive study treatment after slipped dose, if still eligible for treatment.

Escalation to higher OBI-888 dose cohort was not permissible during the study. After a DLT was experienced by patients, dose interruptions, modifications or dose delays may have applied, as per Investigators' judgement (refer protocol section 8.3).

5.1.2 PART B-COHORT EXPANSION

At the time of this version of the SAP, Part A (Dose Escalation) was completed. No DLTs were observed at any dose level tested in Part A, and the MTD was not reached. Therefore, dosing in Part B was initiated at the highest dose tested in Part A (20 mg/kg OBI-888).

Part B was planned to enroll a maximum of 150 additional patients with advanced solid tumors with high Globo H expression (defined as an H-score cutoff ≥ 100 using a validated immunohistochemistry [IHC] assay) across 4 disease-specific cohorts and 1 basket cohort based on a Simon two-stage design. The first stage of Part B recruited up to 9 patients in each cohort (up to 45 patients in the first stage across all cohorts). If sufficient evidence of activity was observed in the first stage, up to 21 additional patients were to be enrolled into that cohort (up to 105 patients in the second stage across all cohorts).

Part B was conducted to obtain additional safety data, characterize the PK and PD profiles of OBI-888, obtain a preliminary assessment of the clinical activity of OBI-888 in Globo H expressing solid tumors, and inform subsequent efficacy-finding clinical development.

The following 5 cohorts of patients who had high expression of Globo H by a qualified laboratory assessment (i.e., Globo H H-score ≥ 100 using a validated IHC assay) were to be enrolled in Part B.

Cohort 1: Pancreatic cancer

Cohort 2: Esophageal cancer

Cohort 3: Gastric cancer

Review Status: Final Version: 2.0 Version Date: 02JUN2022

Cohort 4: Colorectal cancer

Cohort 5: Basket (any solid tumor type other than those included in Cohorts 1 through 4)

All patients were required to provide a tumor biopsy sample, either unstained slides (preferred) or a formalin fixed paraffin embedded (FFPE) tissue block at the initiation of screening visit for screening for Globo H overexpression and confirmation for eligibility of patients for Part B. Patients with a confirmed and documented Globo H H-score of \geq 100 were eligible for the study and were subsequently entered into the 28-day screening period to complete the remaining screening procedures.

Patients were to continue to receive treatment with OBI-888 until progressive disease, unacceptable toxicity, or a decision by the Investigator or patient to discontinue treatment.

5.2 STUDY TREATMENT

OBI-888 was administered as an IV infusion on Days 1, 8, 15, and 22 of each 28-day cycle in Part A and Part B of the study.

For Part A (Dose Escalation), OBI-888 was given at doses of 5 mg/kg, 10 mg/kg and 20 mg/kg to the 3 dose cohorts.

For Part B (Cohort Expansion), patients were to be treated with 20 mg/kg OBI-888 since no DLTs were observed at any dose level tested in Part A, and the MTD was not reached.

Treatment was to continue until progressive disease, unacceptable toxicity, or a decision by the Investigator or patient to discontinue treatment.

OBI-888 investigational drug solution (OBI-888 drug product mixed with saline/glucose infusion solution) was to be administered as an IV infusion by the site staff.

The infusion was to be given for a duration of approximately 90-minutes (±10 minutes), for the initial two cycles (C1 and C2).

The infusion duration from Cycle 3 could be reduced, if no infusion related AEs to prior infusions occurred, to 30 minutes or 60 minutes at the discretion of the Investigator.

5.3 SAFETY REVIEW COMMITTEE

The Safety Review Committee (SRC) for OBI-888-001 study consisted of the clinical lead, medical monitor, and the study Investigator(s) or designee. The SRC was to act in an advisory capacity to monitor patient safety and efficacy during the trial.

This Committee was to convene after each cohort completed the first cycle of treatment during the dose escalation phase, to review safety data (AEs and laboratory toxicities) to determine whether DLTs occurred. Based on DLTs in Part A with consideration of available PK and PD data, RP2D for Part B (Cohort Expansion) was to be recommended by SRC. The SRC was to convene at regular intervals during the conduct of the Cohort Expansion portion of the study to assess safety and activity.

6. RANDOMIZATION AND BLINDING

The study is a Phase I/II, open-label, dose escalation and cohort expansion study and did not involve randomization; patients and members of the clinical study team were not to be blinded to treatment.

Review Status: Final Version: 2.0 Version Date: 02JUN2022

7. SAMPLE SIZE AND POWER CALCULATION

This was a 2-part study: Part A Dose Escalation and Part B Cohort Expansion.

14 patients enrolled in the 3+3 dose escalation phase (Part A).

The cohort expansion phase (Part B) was to enroll up to 150 total patients based on a Simon two-stage design. The first stage was to recruit up to 9 patients in each cohort. If at least 1 objective response was observed within the first 6 cycles of therapy, a second stage recruitment was to occur with up to 21 additional patients enrolled into that cohort, for a total of up to 30 patients per cohort. If at least 4 objective responses were observed within the first 6 cycles of therapy in 30 patients, then OBI-888 was considered worthy of further evaluation in that indication. This design is based on a level of low interest for a treatment with an ORR of 5% versus a level of high interest for a treatment with an ORR of 25%. The sample size was based on a one-sided alpha of 0.05 and 90% power. The two-stage design limits the number of patients treated for a treatment with low levels of activity.

8. ANALYSIS ENDPOINTS

Analysis endpoints are listed as per protocol. Only those endpoints marked with * will be analyzed in the aCSR. Exploratory analyses are to be conducted by OBI Translational Biology (or their designee) and may be included as appendices in the aCSR.

8.1 PRIMARY ENDPOINTS:

- DLTs with OBI-888*.
- AEs/ serious AEs (SAEs) and laboratory abnormalities as graded by National Cancer Institute Common Terminology Criteria for Adverse Events (NCI CTCAE) version 4.03*.
- MTD and RP2D of OBI-888.

8.2 SECONDARY ENDPOINTS:

- Percentage of patients with ORR, CBR*, DOR and PFS according to Response Evaluation Criteria in Solid Tumors version 1.1 (RECIST 1.1).
- Percentage of patients with anti-OBI-888 ADAs in blood*.
- PK and PD parameters of OBI-888*.

8.3 EXPLORATORY ENDPOINTS:

- Globo H and related glycan expression in tumor tissue by IHC.
- ADCC and CDC.
- Identify potential predictive markers by IHC or molecular analysis.
- Tumor Infiltrating Lymphocytes (TILs) including natural killer (NK) cells, and programmed death ligand 1 (PD-L1) expression in tumor tissue samples by IHC.
- Killer cell immunoglobulin-like receptor (KIR), human leukocyte antigen (HLA), and Fc receptor gamma genotype.
- Glycan analysis of OBI-888.

Review Status: Final Version: 2.0 Version Date: 02JUN2022

9. ANALYSIS POPULATIONS

Safety population: all enrolled patients who received at least 1 dose of study drug. This analysis set will be used for all endpoints and analyses except PK.

PK population: all enrolled patients who received at least 1 dose of study drug and had sufficient PK samples (a sample at the end of administration and at least 3 samples during the elimination phase) will be included in the PK assessments. This analysis set will be used for all PK endpoints.

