6.1.1 Part A - Dose Escalation

The dose escalation part of the study will include 3 cohorts of escalating dose levels of 5, 10, and 20 mg/kg, using 3+3 design to identify MTD and RP2D.

Three patients will be enrolled at the lowest dose level. If none of the 3 patients experiences a DLT, the next cohort of 3 patients will be enrolled at the next higher dose level. If 1 of 3 patients in the initial dose cohort experiences a DLT, that cohort will be expanded to 6 patients. If only 1 of these 6 patients has a DLT, then the next cohort of 3 patients will be enrolled at the next higher dose level. If 2 or more patients of the 3-6 patients in a cohort experience a DLT, dose escalation will cease and that dose level will be above the MTD the highest dose where no more than 1 of 6 patients has experienced at DLT. New patients will be enrolled at the previous lower (tolerated) dose level until that cohort has 6 patients. This lower dose level will be considered the MTD if ≤ 1 in 6 patients has a DLT.

Subject should receive all four planned doses with OBI-888 administered during Cycle 1 to be eligible for DLT evaluation, unless they experience a DLT with any dose. A patient who withdraws from the study within the DLT evaluation period for reasons other than drug-related AE will not be included for DLT evaluation and will be replaced; but can continue to receive study treatment after slipped dose, if still eligible for treatment.

Escalation to higher OBI-888 dose cohort is not permissible during the study. After a DLT is experienced by a subjects, dose interruption, modifications or dose delays may apply, as per Investigators judgement (refer protocol Section 8.3).

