8.3 Dose Modifications and Toxicity Management

Escalation to higher OBI-888 dose cohort is not permissible during the study.

Dose modifications for hematologic and non-hematologic toxicity and infusion reactions should be independently assessed at each visit. Recommendations for dose modifications for toxicity are provided in Table 8-1 below.

Toxicity Hold Dose % of Full Dose after **Recovery to Grade 0-1** Grade 1 Do not hold dose 100 75 Grade 2 Hold dose until resolution to Grade 0 or 1 Hold dose until resolution to Grade 0 or 1 Grade 3 75 NA Grade 4 Treatment should be discontinued

 Table 8-1
 OBI-888 Dose Modifications for Toxicity

Once the dose has been reduced for toxicity and found to be well tolerated, re-escalation may be permitted at the Investigator's discretion. If a subject requires dose reductions on more than 2 occasions for toxicity related to OBI-888, the subject should discontinue from the study.

All reasons for treatment modifications should be fully explained.

The study drug dose which is not administered within the permitted window period of ± 3 days, must be skipped, and the next dose will be administered as per protocol schedule. Any skipped dose due to safety reason and if medically justified, for OBI-888 treatment related or unrelated reasons, will not be captured as a protocol deviation for this study.

Treatment interruption for more than 2 consecutive doses for related or unrelated reasons may necessitate discontinuation of study treatment.

Treatment interruption for intercurrent non-treatment related adverse events will be at the Investigator's discretion and based on the well-being of the patient. All reasons for treatment interruption and delays should be fully explained. Treatment for hematologic and non-hematologic toxicity may be implemented as clinically indicated according to institutional guidelines. Refer Table 8-2 for therapeutic antiemetic and anti-diarrheal recommendations.

 Table 8-2
 Therapeutic Antiemetic and Anti-Diarrheal Recommendations

| Diarrhea and Abdominal Cramping | Nausea, Vomiting, or Anorexia |
|---|---|
| Dicyclomine: Recommended when the predominant issue is cramping or abdominal pain | 1st line: 5HT3-inhibitors |
| Diphenoxylate/Atropine or/and Loperamide | 2nd-line: Dexamethasone, ideally in combination with a 5HT3-inhibitor. Short term use can be very effective |
| | Other agents: anti-histamines; benzodiazepines; proton pump inhibitors; dopamine antagonists; cannabinoids |

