14.2 Analysis of Populations

The population to be analyzed will include all enrolled patients who receive at least 1 dose of study drug. This population will be used for all analysis on the safety and clinical activity profile.

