14.5 Safety Analysis

AEs will be coded according to Medical Dictionary for Regulatory Activities (MedDRA) version 19.0 or higher and assessed for severity using CTCAE version 4.03. AEs will be summarized by system organ class and preferred term and presented in decreasing order of incidence. DLTs will also be summarized by dose and cohort. The incidence of TEAEs (events with onset dates on or after the start of the study drug) will be included in incidence tables. Events with missing onset dates will be included as treatment-emergent. If a patient experiences more than 1 occurrence of the same AE, the occurrence with the greatest severity and the closest association with the study drug will be used in the summary tables. SAEs and AEs causing discontinuation will be tabulated. All AEs will be listed by patient, along with information regarding onset, duration, relationship and severity to study drug, action taken with study drug, treatment of event, and outcome.

Vital signs, ECG data, hematology, serum chemistry, coagulation, and urinalysis parameters from baseline and during study will be examined. Treatment emergent changes in key laboratory parameters will be identified. Clinical laboratory data and vital signs will be summarized for each time point evaluated using descriptive statistics including mean values and mean change from baseline values, as well as numbers of patients with values outside limits of the normal range at each time point.

Summary tables will be provided for concomitant medications initiated prior to study enrollment or during the study period.

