10.7 ANALYSIS OF STUDY ENDPOINTS

This section describes analysis of primary, secondary and exploratory endpoints. All endpoints will be analyzed using planned treatments. Summaries will be presented for safety population.

Review Status: Final Version: 2.0 Version Date: 02JUN2022

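### The primary DLT table is placed on all treated Part A patients although the plan limits DLT evaluation to a subset, and the SAP's DLT list departs from the protocol's without naming the differences

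*SAP*

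**What the plan says.** **Population for the table.** SAP 9 defines two sets, safety and PK, and says of the safety set: "This analysis set will be used for all endpoints and analyses except PK". SAP 10.7, which governs the DLT table, adds: "All endpoints will be analyzed using planned treatments. Summaries will be presented for safety population". This follows the protocol. Section 14.2 defines one population of patients with at least one dose and says: "This population will be used for all analysis on the safety and clinical activity profile". Section 14.5, on safety analysis, adds: "DLTs will also be summarized by dose and cohort". Neither document defines a DLT-evaluable set.

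**Rule for DLT evaluation.** Protocol 6.1.1 states: "Subject should receive all four planned doses with OBI-888 administered during Cycle 1 to be eligible for DLT evaluation", with an exception for a patient who has a DLT. A patient who withdraws in the DLT period for a reason other than a drug-related AE is, in the words of SAP 5.1.1, one who "was not included for DLT evaluation and was to be replaced". Both sections allow such a patient to stay on treatment after a missed dose if still eligible.

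**DLT criteria.** Protocol 6.2 and SAP 10.7.1 each give a list, and the lists are not the same. SAP 10.7.1 says DLTs are taken as recorded on the eCRF and not derived by program. SAP 11 says only that the eCRF criteria are analysed, and the revision history says only that the categories were changed to match the eCRF.

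**The concern.** DLT is the first primary endpoint, and SAP 8.1 stars it for the abbreviated report. Part A recorded no DLTs. With a zero numerator, what the table tells a reader is how many patients were evaluated at each dose and against which criteria. The plan leaves both unclear. The table's population includes patients whom the plan's own rule says were not evaluated, and the criteria printed beside the table are not those in the protocol.

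The rule can exclude treated patients in practice. Protocol 8.3 deals with "The study drug dose which is not administered within the permitted window period" by requiring it to be skipped. A treated patient can therefore miss a Cycle 1 dose, become non-evaluable for DLT, and remain in the safety population.

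**Working it through.** **1. The plan's own figure.** Protocol 14.1 allows up to 18 patients in Part A. Three dose levels with at most 6 patients each gives 3 × 6 = 18, which reproduces it. The documents state no DLT-evaluable count.

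**2. Inputs.**
- Part A patients enrolled: 14 (SAP 7).
- DLTs: 0 (protocol 4.3.1, SAP 5.1.2).
- Evaluable patients needed to pass a dose with no DLT: 3 (protocol 6.1.1).
- Patients needed to declare an MTD: 6 at that dose, with at most 1 DLT (protocol 6.1.1).

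**3. Numerator.** A patient with a DLT is evaluable by definition. The count of DLTs is therefore the same on either set, and only the denominator can differ.

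**4. Denominator, assuming the 3+3 rule was followed.**
- Three evaluable patients per dose: minimum 3 + 3 + 3 = 9. The excess in N is 0 to 14 − 9 = 5, at most 5/14 = 36%.
- Top dose filled to 6: minimum 3 + 3 + 6 = 12. The excess is 0 to 14 − 12 = 2, at most 2/14 = 14%.

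The documents do not settle which case applies. SAP 10.7.1 C says 20 mg/kg was identified as the MTD, which under protocol 6.1.1 would need 6 patients. SAP 5.1.2 says the MTD was not reached.

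**5. Evidence on the true number.** Protocol 4.3.1 gives ADA incidence as 1/5 and 1/3 for the first two cohorts. If those denominators are the cohort sizes (an assumption), the top dose had 14 − 5 − 3 = 6 patients. The two patients beyond three at 5 mg/kg would then fit replacement of non-evaluable patients, but nothing confirms it. The same section reports trough accumulation in 12 of 14. This suggests repeated dosing in most patients but does not show that all four Cycle 1 doses were given. The number non-evaluable may be zero.

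**6. Illustration only, since the SAP plans no interval for DLTs.** The exact two-sided 95% upper limit for 0/n is 1 − 0.025^(1/n):

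| n | Upper limit |
|---|---|
| 14 | 23.2% |
| 12 | 26.5% |
| 9 | 33.6% |

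**7. The two DLT lists side by side.**

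| Item | Protocol 6.2 | SAP 10.7.1 |
|---|---|---|
| Thrombocytopenia | Grade 4, or Grade 3 if there is bleeding | Grade 4 only |
| Infusion reactions | No separate item | Grade 4, or recurrent Grade 3 or higher despite a slower rate and supportive care |
| Other non-hematological, Grade 3 or higher | Any other event unresolved by the next infusion | Any event, with an exception for nausea, vomiting or diarrhea placed before the resolution clause |

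The first two differences are substantive. Grade 3 or higher bleeding that does not resolve could still qualify under the SAP's non-hematological item. Grade 3 thrombocytopenia with lower-grade or resolved bleeding meets no SAP item. A Grade 4 infusion reaction that resolves before the next infusion meets the SAP's infusion item but not the protocol's non-hematological item. The third difference may be intended as equivalent.

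**The case against.** **The SAP supersedes the protocol.** Protocol section 14 says so where the two differ. That may settle which DLT list governs the table. It does not settle the denominator, because that conflict lies inside the SAP, between 5.1.1 and sections 9 and 10.7. Nor does it say which list was applied when zero DLTs was first reported: protocol 4.3.1 gives results as of March 2020, and SAP version 1.0 is dated 31 August 2021.

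**The denominator may correct itself.** SAP 10.1 makes non-missing observations the default for percentages, and DLTs are taken from the eCRF. If the eCRF field is blank for non-evaluable patients, they could drop out of the percentage. The field is not shown, so an excess is likely but not certain. This objection stands in part.

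**The information is largely in the listings.** SAP 10.8.1 lists dosing by patient with reasons for missed doses, 10.4 lists dosing dates and reasons for discontinuation, and 10.7.1 B lists all AEs with DLTs flagged. A careful reader could largely rebuild evaluability for 14 patients. This stands. The gap is that the table itself would not show it. A reader might infer that evaluability could not be recovered at all; these listings do not support that.

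**Only one table is affected.** The DLT table by system organ class and preferred term carries no asterisk in 10.7.1 B, so it is not part of the abbreviated report. This also stands.

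**The use of eCRF criteria is disclosed.** It is, in SAP 11 and the revision history, but no difference is named.

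**Conclusion.** The point holds and is minor. The plan puts the primary DLT table of SAP 10.7.1 A on a population that its own evaluability rule does not support. If any of the 14 were non-evaluable, the N shown would probably be too high. The total excess is 0 to 5 patients on the widest case, or 0 to 2 if the top dose was filled to 6. Both ranges assume that the 3+3 rule was followed, and the true figure may be 0. Confidence is high in the conflict of text and lower in its effect on the printed denominator. The DLT list differs from the protocol's in three unnamed places, one of them possibly only wording.

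A reader might infer more: that DLTs were missed, that five patients were in fact non-evaluable, or that the dose decision is unsound. The documents support none of these. The observed rate is 0% on any denominator, and no event meeting only one list is reported. The dose was settled in Safety Review Committee review, not from this table.

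**What to change.** 1. Add a DLT-evaluable set to SAP 9, using the rule already in SAP 5.1.1, and make it the denominator of the 10.7.1 A table.
2. Report treated, evaluable and replaced patients at each dose. Note in SAP 11 that this refines protocol 14.2 and 14.5 for that table.
3. Reconcile SAP 10.7.1 with protocol 6.2. No view is taken here on which list is right. Name each of the three differences in SAP 11, and state which list the zero count refers to.
4. Check the existing Part A Cycle 1 AE and laboratory data against both lists, and report any event that meets only one.

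The cost is low: SAP wording, one flag on 14 patients from dosing data already planned for listing, and a short check of data in hand. No new data are needed.
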